In cost-effectiveness analysis the effect is measured in health units (or other outcome measures depending on the context). The outcomes are common health measures in natural units, and the results are presented as cost per effect unit/outcome measure. In cost-utility analysis, also called cost per QALY analysis, the effect is measured as quality-adjusted life years (QALYs) on a scale of 0 (death) and 1 (full health). A quality-adjusted life year (QALY) captures both life years gained and improved health as a result of treatment [8, 9].

The economic evaluation will be measured at society level.

Costs and QALYs will be measured for each phase of 6 months

The cost-effective analysis will relate the difference in total mean costs at societal level per 6 months between all intervention -and usual care phases to the difference in RUD, RSS, QoLs, QALYs, NPI, function level such as ADL and IADL

The analysis will use a discounting rate at 3.5%.

Following other costs studies calculating RUD in an advanced economy setting, our analysis will use 35% of the Norwegian average income to value lost leisure time for retired caregiver.

The primary economic evaluation will use the opportunity cost method to assess the costs of informal caregiving. For a sensitivity analysis, the replacement cost will be used.

Unit costs will be based on information from Statistics Norway and information from the primary health care institutions in each municipalities.

Covariates and strata

In the main statistical analyses, the following covariates are used for both caregivers and PwD.

For PwD: Age, sex, marital status, cohabitation status, number of co-caregivers, clinical characteristics of dementia (dementia etiology, neuropsychiatric symptoms, functional level)

For Caregivers: Age, sex, marital status, cohabitation status, numbers of co-caregivers involved in caregiving for the PwD, work status, use of health care services,

Groups, municipalities

Municipalities will be grouped in the main analysis and used as an adjustment variable (fixed effects). This is not the case for district municipalities as we consider that the dyads are similar within municipalities

Subgroups

In subgroup analyses, the following covariates will be used to define relevant subgroups:

- Gender (male, female)
- Work (retired and working caregivers)
- Caregiver relation (spouse, children)
- Residency (living alone, or with caregiver)

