- Formal caregiver (whether dyads are receiving care by home nursing)
- Categories of caregiver burden intensity
- Categories of dementia diagnoses

Results from subgroups will be presented for the primary analyses.

Observation and analysis times

Study periods

Timeline															
Groups/participants	Inclusion period	Control group			Kristiansand 3, N=35			Bærum 3, N=35			Bergen 3, N=35				
					Kristiansand 2, N=35										
					Bærum 2, N=35										
					Bergen 2, N=35										
		Kristiansand 1, N=35						Follow up							
Number of months		0	1 2	3 4	5 6	7 8	9 10	11 12	13 14	15 16	17 18	19 20	21 22	23 24	
Date		01.09 2019		01.03 2020		01.09 2020		01.03 2021							

		STUDY PERIOD							
		Enrollment		Allocation	Post-allocation				Close-out
TIMEPOINT	-t	0		t1	t2	t3	t4	t5	
ENROLLMENT:									
Eligibilityscreen	x								
Informed consent	x								
Allocation		x							
INTERVENTIONS:									
1st group			x	x					
2nd group				x	x				
3rd group					x	x			
ASSESSMENTS:									
Baseline variables			x						
Outcome variables				x	x	x	x	x	

The stepped wedge randomized control design. A) The randomization in time takes place at month 0. First group (red) is in the intervention period from month 1 to 6, second group (yellow) from month 7 to 12, third group (green) from month 13 to 18. Implementation seminars will be held at month 0, 6 and 12, midway evaluation at month 3, 9 and 15. Data will be collected at baseline (month 0), after first intervention period (month 6-7), after second intervention period (month 12-13), after third intervention period (month 18-19) and at end of study at 24 months. B) Schedule of enrollment, interventions and assessments over the study period.

Demographics and Background Characteristics

Demographics and baseline characteristics

The following demographic characteristics will be presented descriptively and listed for both PwD and caregiver:

- Sex (male, female)
- Age in years
- Marital status (spouse, child)
- Work status (employed, unemployed, retired)
- Number of co-caregivers
- MMSE total score
- RUD (number of care hours the last 30 days)
- RSS total score
- NPI total score
- QoL total score

Date of informed consent and protocol version will be listed

Medical history

We will provide information on the number of years since formal diagnosis of dementia together with descriptive statistics.

Exposure and Compliance

Treatment groups

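### The 3.5% discount rate has no stated time origin or scope; if counted from trial start it makes identical costs and QALYs look about 1.1% to 2.6% lower under LIVE

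*SAP*

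**What the plan says.** Under Economic evaluation, the SAP sets the measurement unit: "Costs and QALYs will be measured for each phase of 6 months". It then defines the cost side of the comparison: "The cost-effective analysis will relate the difference in total mean costs at societal level per 6 months between all intervention -and usual care phases". This cost difference is set against a list of effects, QALYs among them: "to the difference in RUD, RSS, QoLs, QALYs, NPI, function level such as ADL and IADL". Next comes the discounting sentence: "The analysis will use a discounting rate at 3.5" per cent. No base date, timing convention (start, middle or end of phase) or list of discounted quantities is given.

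The phase calendar is in the Study periods section: "First group (red) is in the intervention period from month 1 to 6, second group (yellow) from month 7 to 12", and "third group (green) from month 13 to 18". Outcomes are collected "after third intervention period (month 18-19) and at end of study at 24 months", so there are four 6-month phases. No group returns to usual care. The effect table under Intervention effect has the same layout: its only empty cells are group 2 at the first time point and group 3 at the first two.

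The economic section mentions no period adjustment. Model (1) under Causal model shows no period term, although the same section calls adjustment for time-related confounders important.

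**The concern.** Discounting is meant for streams of cost and benefit that follow from one starting decision. Here the quantity compared is an average per 6-month phase, and the trial month in which a phase falls is fixed by the allocated sequence. Discounting to trial start gives later phases smaller weights. Because LIVE phases are later on average, they shrink more than usual-care phases even when nothing differs between them.

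The result would be a false saving in costs and, if QALYs are discounted too, a false loss in QALYs. Both are differences of the kind that form the ICER, which the SAP lists under its primary objective. A distortion that is small against total cost can still matter against a small difference in cost or QALYs.

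**Working it through.** The SAP reports no economic result, so there is no figure of its own to reproduce. The check asks what the stated rate does to values that are the same in every phase.

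**Inputs.**
- Rate 3.5% (SAP), taken as annual (assumption).
- Four 6-month phases; LIVE starts in phase 1, 2 or 3 for groups 1, 2 and 3 (Study periods).
- Equal group sizes: the timeline shows 35 dyads per municipality in each sequence.
- Usual-care phases: group 2 phase 1; group 3 phases 1 and 2. Mean phase (1+1+2)/3 = 1.33.
- LIVE, active only: phases 1, 2, 3. Mean phase 2.00.
- LIVE with follow-up: phases 1; 2, 2; 3, 3, 3; 4, 4, 4. Mean phase 26/9 = 2.89.

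**Discount factors.** With mid-phase timing from trial start, the factor is 1.035^(−t) at t = 0.25, 0.75, 1.25 and 1.75 years: 0.9914, 0.9745, 0.9579 and 0.9416.

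| Phases averaged | Mean factor | Relative to usual care |
|---|---|---|
| Usual care: (2×0.9914 + 0.9745)/3 | 0.9858 | – |
| LIVE, active only: (0.9914 + 0.9745 + 0.9579)/3 | 0.9746 | −1.13% |
| LIVE with follow-up: (0.9914 + 2×0.9745 + 3×0.9579 + 3×0.9416)/9 | 0.9599 | −2.63% |

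**Other timing conventions.** Start-of-phase and end-of-phase discounting multiply every factor by the same constant, so the percentages are unchanged. Whole-year steps (factor 1 in year 1, 1/1.035 in year 2) give −1.13% and −2.25%.

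**In QALYs.** At an assumed utility of 0.7, one phase is worth 0.5 × 0.7 = 0.35 QALY.
- Active only: 0.35 × (0.9746 − 0.9858) = −0.004.
- With follow-up: 0.35 × (0.9599 − 0.9858) = −0.009.

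**In costs.** For an assumed 100,000 per phase, the false saving is about 1,100 to 2,600.

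**Net direction.** Let C be the common cost per phase, Q the common QALY per phase, λ the value placed on a QALY, and d the gap between the two mean factors (0.011 or 0.026). The false change in net benefit for LIVE is dC − λdQ = d(C − λQ). Its sign depends on whether C exceeds λQ. The SAP gives none of these three values.

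**When the artefact vanishes.**
- No discounting of the phase contrast: 0.
- Each phase discounted only to its own start: every phase has the same factor, so the relative difference is 0.
- Discounting to trial start, with period effects in the comparison: regressing the discounted constants on period indicators and a LIVE indicator gives a LIVE coefficient of 0 (to rounding).

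**The case against.** The strongest objection is that the SAP never says phases are discounted to trial start. A reader might infer that the plan as written biases its economic result. The document does not go that far: the rule is incomplete, and discounting each phase to its own start would be harmless. The rate might also be meant for the simulation model mentioned among the sensitivity analyses, although the SAP does not link the two. This objection stands as far as it goes. It leaves a sentence that either distorts the phase contrast or does virtually nothing to it, so it needs attention either way.

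Four further inferences are not supported.
- *Usual care always comes first.* That holds only within dyads of groups 2 and 3. Group 1 has no usual-care phase after baseline, and its LIVE phase runs alongside usual care in the other groups. Only the average timing differs, and the calculation already reflects this.
- *The shrinkage can be set against the 7 h/week in the sample size section.* That target concerns RUD hours as an efficacy outcome. Discounting appears only in the economic section, and nothing says efficacy hours are discounted.
- *The larger figure is the plan's figure.* The 2.6% depends on counting follow-up as LIVE. The effect table and the endpoint definition favour that; the calendar, which labels follow-up separately, favours 1.1%. The SAP does not settle it.
- *A trial with no effect would report a false economic result.* The economic evaluation runs only if an effect is found on a primary or secondary outcome. The artefact would therefore usually add to a real difference.

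It is also fair to say that the missing period adjustment is a separate problem and probably a larger one. Any time trend over 24 months, such as disease progression or the pandemic, enters the same phase contrast. The SAP gives no figure from which to size it.

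**Conclusion.** The point holds in a limited form and is minor. The SAP attaches a 3.5% rate without origin or scope to a contrast of 6-month phase means. On the natural reading, discounting to trial start, identical costs and QALYs appear 1.1% lower (active phases only) to 2.6% lower (with follow-up) under LIVE. This rests on an annual rate, equal sequence sizes, the calendar as printed, and no period adjustment in the economic comparison; the QALY size also rests on the assumed utility. If only costs are discounted, only the false saving remains. The postponement in two municipalities described under Modification History would widen the timing gap if it prolonged usual care, but the SAP does not give the revised dates.

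The conclusion is not that the economic result will favour or disfavour LIVE. The cost and QALY artefacts pull in opposite directions, and the documents do not determine which prevails.

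**What to change.** Replace the discounting sentence with one stating that the within-trial contrast of 6-month phases is not discounted, and that 3.5% per year applies only to a model or projection that runs both strategies from one common time origin over more than a year. State which quantities are then discounted, and whether follow-up phases count as intervention phases.

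Separately, include period effects in the cost and QALY comparison. That alone would remove the discounting artefact, and it would also address the time confounding that the sentence change leaves in place.

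The cost is a sentence or two in the SAP and one set of terms in a regression, with no new data. Compared with discounting to trial start, the change removes a false saving and a false QALY loss, so the reported ICER may move either way.

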Efficacy: primary	x		
Efficacy: secondary	x		x
Efficacy: other	x	x	x

General Statistical Methods and Definitions

General statistical methods

The statistical analysis will be presented by treatment group for the different analysis sets as outlined in section 4.

Stepped wedge design (SWD) do not strictly feature a treatment and control group, and thus, the summary statistics will include all participants at baseline, and the characteristics according to intervention sequences.

Continuous variables will be summarized using descriptive statistics (means and interquartile ranges), and categorical variables will be presented by frequencies and percentages. A table will present the number of caregivers and PwD with the following data: missing values, mean, median, standard deviation and confidence intervals.

Means and median as well as percentages will be presented with 1 additional decimal place and standard deviation by 2 additional decimals.

If the number of PwD or caregivers in a category is 0, then percentage will not be displayed.

P-values will be reported to 3 decimal places.

Unless otherwise specified, all statistical tests will be two-sided.

Causal model

Due to the longitudinal structure of the collected trial data, we considered the following linear mixed model to estimate and identify the treatment effect due to the intervention. Our SWD, consisting of $j = 3$ municipalities and 3 steps, is a closed cohort design, and thus, time related confounders are important to adjust for [5] when assessing treatment effect.

Mixed-effects regression is one of the most common approaches when estimating the intervention effect in SWD [6, 7]. In our design, we will consider the following model as our primary analysis model, assuming a constant treatment effect.

$$(1) Y_{ijt} = \beta_0 + O_{ijt}\beta_1 + X_{ijt}\beta_2 + b_i + \epsilon_{ijt}$$

where notation Y_{ijt} refers to the primary outcome caregiver burden (RUD and RSS), elaborated in section 3 Study Design, for individual i nested in municipality j at time point t . O_{ijt} is the treatment indicator (effect of receiving assistance from a municipality coordinator) and β_1 is the average treatment effect parameter of interest. Since the study collects repeated observations from the same participants, we consider a longitudinal regression model that adjusts for participant-level random effect, $b_i \sim N(0, \sigma_b^2)$, which corresponds to a compound symmetric correlation structure.

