$\epsilon_{ijt} \sim N(0, \sigma_\epsilon^2)$ represents random error that changes across t and i .

X_{ijt} constitutes control variables which are demographic, socio-economic and clinical confounders (age, sex, caregiver marital status, work status, ADL function), and stratification variables used in the design stage.

Due to the non-normal distribution of hours and costs we will use both linear mixed-effects, as well as general lineal mixed regression model for assessing both primary variables. For RSS, and other continuous variables, we use Linear Mixed regression model. Log-transformation of the outcome will also be considered to address potential non-normality in the response.

Intervention effect

In secondary analysis, we will further examine the extent to which the treatment effect will depend on the calendar time when COVID lockdown happened, and the potential for delayed effect. We collectively refer these effects as heterogeneous treatment effect, and provide a schematic illustration following Section 3.2 of Li et al. (2020) [6]. The rationale is that there the lockdown during the pandemic may contribute to change in the intervention effect. In addition, the intervention may be most effective when it is first introduced, and the sustained effect may be smaller. Therefore, when modelling the intervention effect, we will allow for heterogeneous effect and assess the robustness of our primary analysis. The table below shows how the intervention effect can differ between periods (t) across different groups (g). The deltas (δ) constitute the intervention effect, and their subscript defines heterogeneous effects where δ_0 is the pre-lockdown intervention effect, δ_0^* is the intervention effect post-lockdown, and δ_1^* is the follow-up post-lockdown treatment effect.

When modelling the intervention effect, we will test the null-hypothesis (H_0)

$$\delta_0 = \delta_0^* = \delta_1^*$$

	$t = 1$	$t = 2$	$t = 3$	$t = 4$
$g = 3$			δ_0^*	δ_1^*
$g = 2$		δ_0^*	δ_1^*	δ_1^*
$g = 1$	δ_0	δ_1^*	δ_1^*	δ_1^*

Economic evaluation

If we identify an average treatment effect on one of the primary and secondary outcomes, we will use cost-efficiency (CEA) and cost-utility analysis (CUA) to evaluate the economic effects of the LIVE treatment.

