The definition of treatment assignment as specified in section “Analysis sets” will be used in this section, too.

Deviations from the randomized treatment sequence occurred under the first Covid-19 lockdown, see section Modification History, Changes to the study protocol

Treatment duration

Each municipal coordinators are writing logs, and we will collect the data and calculate total hours of care by the coordinator, divided into different categories.

Descriptive statistics for the total hours of care by the coordinators will be presented.

Delivery of the intervention

One coordinator from the municipal per dyad

Efficacy

Primary efficacy analysis

The primary efficacy analysis variable caregiver burden is based on two variables. The first is RUD, divided in three categories: number of hours the last 30 days invested in personal, instrumental and supervisory care. The second is RSS measured as total score but also

specific and clustered items. Lower hours of informal care as well as lower score of RSS, indicates reduction in caregiver burden.

The null hypothesis states that there are no differences in burden and resource utilization between the LIVE intervention and usual care. The primary alternative hypothesis (H1) states that the LIVE intervention will improve caregiver burden and resource utilization compared with usual care. The secondary alternative hypothesis (H2) is that the LIVE intervention will provide more cost-efficient services than usual care.

H0: LIVE treatment = control

H1: LIVE treatment > control

H2: cost efficiency > control

where LIVE treatment denotes the proportion of caregivers experiencing improvement in care burden. The primary hypothesis will be statistically assessed by means of a χ^2 test on the one-sided significance level of 2.5% (corresponding to 5% two-sided).

We will plot the regression line to visualize the parallel effect for both treatment group and control group.

The significance level will be set to 2.5% (one-sided, corresponding to 5% two-sided), the corresponding level of one-sided CI is 97.5% (corresponding to 95% two-sided).

Missing data

We will pre-specify a list of baseline covariates that are likely associated with the missingness and the outcome, and adjust for these covariates in our primary analyses. This covariate-adjusted analysis will be valid under the missing at random (MAR) mechanism.

Sensitivity and robustness tests of regression analyses and economic evaluation

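### Baseline MMSE, the only cognitive-severity measure in the SAP, is named in no adjustment list; adding it is a small, low-cost improvement

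*SAP*

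**What the plan says.** Four places in the SAP bear on this.

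- **Demographics and baseline characteristics.** "MMSE total score" is one item in a list introduced with "The following demographic characteristics will be presented descriptively and listed for both PwD and caregiver". This is the only mention of MMSE.
- **Causal model, model (1).** The control variables for the primary outcomes RUD and RSS include "clinical confounders (age, sex, caregiver marital status, work status, ADL function), and stratification variables used in the design stage". MMSE is not among them.
- **Covariates and strata.** The list for the person with dementia ends with "clinical characteristics of dementia (dementia etiology, neuropsychiatric symptoms, functional level". The caregiver list ends with "numbers of co-caregivers involved in caregiving for the PwD, work status, use of health care services". Neither contains MMSE.
- **Missing data.** "We will pre-specify a list of baseline covariates that are likely associated with the missingness and the outcome", it says, and these will be adjusted for in the primary analyses. It then states: "This covariate-adjusted analysis will be valid under the missing at random (MAR) mechanism". No variable is named.

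No other cognitive scale appears. GDS is a depression scale, CGIC rates change, and years since diagnosis is not a measure of cognition.

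**The concern.** In a dementia trial whose primary outcomes include hours of supervisory care, baseline cognition can be expected to predict the outcome. It may also predict who is lost over 24 months. That is the test the SAP sets for its missing-data covariates, yet the one cognitive score it holds is used only for description.

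Two things are at stake, both modest. One is precision: a prognostic baseline score that explains part of the between-dyad variance narrows the interval for the treatment effect. The other is protection against bias if dyads with worse cognition are lost at different rates in usual-care and LIVE time, since the model then conditions on no direct measure of cognition. Settling the status of MMSE before the analysis also removes a choice that could otherwise be made after the results are seen.

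**Working it through.** **Inputs from the SAP (Sample size estimation):** effect 7 h/week, SD 20 h/week (variance 400), 80% power, 5% two-sided, 3 sequences, 5 periods, within-individual correlation 0.1075, 315 dyads planned.

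**The SAP's own figure.** Two means: 2 × (1.960 + 0.842)² × 400 / 49 = 2 × 7.849 × 8.163 = 128.1, so 129 per arm and 258 in total. The t-based version gives 130 per arm, 260 in total. The stated 260 reproduces. The present point does not depend on it.

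**Step 1. Variance of the treatment effect in this design.** Treatment patterns over the five visits are 0 1 1 1 1, 0 0 1 1 1 and 0 0 0 1 1. I assume a random intercept (variance τ²), residual variance σ² and period effects. Model (1) does not write period effects out, but its text calls for adjustment for time. With U = 9 (treated cells), W = 0 + 1 + 4 + 9 + 9 = 23 (squared column sums), V = 16 + 9 + 4 = 29 (squared row sums), I = 3 and T = 5:

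- I·U − W = 27 − 23 = 4
- U² + I·T·U − T·W − I·V = 81 + 135 − 115 − 87 = 14
- Var = 9σ²(σ² + 5τ²) / [N(4σ² + 14τ²)]

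At correlation 0.1075, τ² = 43 and σ² = 357. Then N × Var = 9 × 357 × 572 / 2030 = 905.3, and N for 80% power = 905.3 × 7.849 / 49 = 145.0. This is only a reference value for relative change. The SAP's own requirement for its stepped-wedge calculation is 240.

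**Step 2. MMSE added with no other severity covariate in the model.** If it removes 10%, 25% or 50% of τ², N falls from 145.0 to 143.8, 141.9 or 138.3, a variance reduction of about 1-5%. At assumed correlations of 0.3 and 0.5, N goes from 126.9 to 125.8-119.4 and from 96.1 to 95.5-91.7, about 1-6%.

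**Step 3. MMSE added when function is already in the model.** This is the relevant comparison, since model (1) names ADL function. Let a and b be the correlations of function and of MMSE with the dyad effect, and ρ their correlation with each other. Function alone explains a² of τ². Both together explain (a² + b² − 2abρ)/(1 − ρ²). Assumed ranges: a and b 0.3-0.7, ρ 0.4-0.6.

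- Low: a = 0.5, b = 0.3, ρ = 0.6. (0.25 + 0.09 − 0.18)/0.64 = 0.25 = a². MMSE adds nothing.
- Middle: a = b = ρ = 0.5. (0.25 + 0.25 − 0.25)/0.75 = 0.333 against 0.25. At correlation 0.1075, τ² goes from 32.25 to 28.67 and N × Var from 885.9 to 878.8, a fall of 0.8%.
- High: a = 0.3, b = 0.7, ρ = 0.6. (0.09 + 0.49 − 0.252)/0.64 = 0.5125 against 0.09. At correlation 0.1075, τ² goes from 39.13 to 20.96 and N × Var from 898.7 to 861.9, a fall of 4.1%. At correlation 0.3 (τ² from 109.2 to 58.5, σ² = 280), N × Var goes from 785.8 to 744.0, a fall of 5.3%.

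The gain is therefore roughly 0-5% in variance.

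**Step 4. Bias when loss depends on severity but not on treatment.** Simulation with 315 dyads, about 20% loss, severity explaining 30% of between-dyad variance, and a true effect of −7. At correlation 0.1075 the mean estimate is −6.94 without severity and −6.90 with it (Monte Carlo SE 0.10). At 0.5 it is −7.00 in both. The standard errors are 1.773 against 1.749 and 1.455 against 1.437, that is 1.4% and 1.3% larger without it. No bias is visible.

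**Step 5. Bias when the dependence differs by treatment.** Assumed loss per period: the lowest MMSE third at 20-30% under usual care, the rest at 5%, and everyone at 10% under LIVE. With no severity covariate, the estimate at correlation 0.1075 is −6.82 to −6.56. With MMSE it is −6.89 to −7.00, a shift of 0.10-0.43 h/week. With one functional covariate already in the model, adding MMSE shifts the estimate by about 0.02-0.33 h/week. The standard error at 315 dyads is about 1.4-1.7, so the largest shift is 0.33/1.7 = 0.19 to 0.33/1.4 = 0.24 of a standard error.

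**The case against.** The strongest case against is that this is a matter of preference. Dyads are individually randomized, model (1) "adjusts for participant-level random effect", and dementia etiology, neuropsychiatric symptoms and function already carry part of the severity. Not adjusting for one prognostic score is a legitimate choice. That stands, and it limits the point to a recommended improvement.

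A reader might infer that the missing-data adjustment excludes MMSE. The SAP does not say so. The list is promised and left empty, and because its covariates are to enter the primary analyses, MMSE could still come in under the present text.

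A reader might also infer that the listed severity measures are unsuitable because they are trial outcomes, while MMSE is safe. That contrast fails: baseline function and baseline NPI cannot be changed by treatment either. The time subscript on the control variables in model (1) leaves open a time-varying ADL value, but that is a separate question which adding MMSE does not settle.

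The pattern in step 5, with loss tied to cognition under usual care only, is assumed. Nothing in the SAP describes it.

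Finally, the change is not entirely free. A standard mixed model drops dyads with a missing covariate, and the SAP gives neither MMSE completeness nor a rule for missing covariates. Since variance is proportional to 1/N, dropping 1% of 315 dyads (about 3) cancels a 1% gain, and dropping 5% (about 16) cancels the largest gain.

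**Conclusion.** The point holds as a minor improvement. MMSE is a listed baseline variable, it is the only cognitive-severity measure in the SAP, it plausibly meets the SAP's own criterion for a missing-data covariate, and no adjustment list names it. With function already adjusted for, adding it lowers the variance of the treatment effect by roughly 0-5%. It reduces bias by about 0.0-0.3 h/week against a planned effect of 7, and only if loss by cognitive severity differs between usual-care and LIVE time.

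These sizes rest on assumed correlations and loss rates that the SAP does not give. The documents do not support saying that the primary estimate is biased as planned, or that the planned model is invalid without MMSE.

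**What to change.** - **Covariates and strata:** add baseline MMSE total score of the person with dementia, as a continuous covariate, to both the person-with-dementia list and the caregiver list. The caregiver list matters because RUD and RSS measure the caregiver's time and burden.
- **Causal model:** carry the same term into the control variables of model (1), so that the two sections agree on it.
- **Missing data:** name baseline MMSE in the promised list.
- **Missing MMSE values:** state a simple rule, for example imputation of the baseline value, so that no dyad leaves the analysis for want of this score.

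The cost is a few lines of SAP wording, fixed before the final analysis. MMSE is already among the baseline variables, so no new data collection is needed.
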